Protocol Title: Safety and Tolerability Study of Antimicrobial TheraGauze for Skin Abscess - Pilot Study

Phase of Study: I

Version date: 30March2017

Funding for this project is from the Department of Defense, through Soluble Systems, LLC

Principle Investigator: [name]  
Eastern Virginia Medical School  
[name]  
[name]  
[contact]  
[contact]  
[contact]  
Email: [[contact]](mailto:[contact])

Institutional Review Board: Eastern Virginia Medical School IRB (FWA00003956)

**Background.** Skin infections resulting in abscess, furunculosis, have become increasingly common in the past decade with the rapid emergence of community-associated methicillin-resistant *Staphylococcus aureus* (MRSA). The increasing incidence of these skin infections has stressed the medical system at the primary care, urgent and emergent care levels at significant cost. Methicillin-resistant *S. aureus* (MRSA) killed 18,650 Americans in 2005, exceeding the number of deaths attributable to HIV/AIDS (Klevens, Morrison et al. 2007). MRSA infections were identified for 368,600 hospital stays in the U.S. in 2005 for an estimated \$5 billion in hospitalization costs (Healthcare Cost and Utilization Project, DHHS).

The primary endpoint of the study is to evaluate the safety of and identify side effects of TheraGauze/tobramycin wound packing compared with standard of care management for cutaneous abscesses requiring incision and drainage. Current standard of care in most emergency and urgent care settings for community-acquired skin abscess is incision and drainage followed by packing with cotton wick ( $\pm$  iodoform) and anti-MRSA systemic antibiotics given orally for 5 – 7 days (Mistry, Weisz et al. , LoVecchio, Perera et al. 2009). Commonly prescribed oral antibiotic regimens include trimethoprim-sufamethoxazol, doxycycline, and clindamycin. Common side effects from these systemic antibiotics include diarrhea (~20%), nausea, and rash (Powell and Wenzel 2008). Uncommon but severe side effects include *C. difficile* colitis, Stevens-Johnson Syndrome, toxic epidermal necrolysis, hepatitis, and aplastic anemia (Bell, Foster et al. , Mistry, Schwab et al. 2009).

The primary likely benefit of this novel therapeutic strategy is avoiding the side effects of systemic antibiotics that cause significant additional morbidity and medical expense. Other possible benefits of this novel strategy are improved wound healing time and less scar formation. This work will capitalize on the polymer structure of TheraGauze that provides a platform for fluid redistribution within the wound bed without causing skin maceration (Landsman 2008). We have developed an antimicrobial form of TheraGauze by loading TheraGauze with tobramycin (TheraGauze+tobramycin). Prior in vitro testing demonstrated potent and sustained antibacterial activity for TheraGauze+tobramycin against a wide range of bacterial pathogens, including all strains of community-associated MRSA tested (Echague, Hair et al. 2010). Lack of systemic absorption is a well-established property of tobramycin. Thus, high concentrations can be delivered locally in the wound greatly exceeding typical minimum inhibitory concentrations (MICs) without concern for systemic toxicity. Additionally, tobramycin is a highly bactericidal antimicrobial compound. Tobramycin is rarely used as a systemic antibiotic now having been largely replaced by fluoroquinolones. Therefore, selective pressure that could promote development of antibiotic resistance and compromise systemic antibiotic therapy is not a concern.

Tobramycin has been used for many years both as topical therapy applied to the eyes as well as in surgical wounds as tobramycin-containing polymethacrylate beads. Topical application of tobramycin to cutaneous wounds has also been reported without evidence of local or systemic toxicity. Andrew et al reported application of 3% (w/v) tobramycin with dexamethasone (i.e., Tobradex) ointment applied to post dermatological procedure surgical wounds twice-a-day for 2 weeks. Eighteen human subjects were enrolled and no local or systemic side effects were noted (Andrew, Luecke et al. 2012)

In 2003 Simplex P with tobramycin was the first FDA approved antibiotic impregnated bone cement ([www.stryker.com](http://www.stryker.com)). Preparations of tobramycin-impregnated bone cement appear to generally range from 1g to 1.2g in 20 ml (50 – 60 mg/ml) (Sterling, Crawford et al. 2003, McLaren, McLaren et al. 2008). Tobramycin is reported to be the antibiotic of choice for bone cement for more than 75% of orthopedic surgeons (Fish, Hoffman et al. 1992) with excellent local tobramycin levels and minimal systemic tobramycin levels (Soto-Hall, Saenz et al. 1983, Eckman, Henry et al. 1988, Davies and Harris 1991, Pritchett and Bortel 1992, Brien, Salvati et al. 1993, Sterling, Crawford et al. 2003, McKee, Li-Bland et al. 2010). Despite the extensive literature on tobramycin bone cement there are no mentions of local toxicity. It is notable that so little toxicity has been reported given the significantly varying amounts of tobramycin cement are used for different types of orthopedic procedures and depending on the amount of bone being replaced. The wounds the tobramycin cement are in deep tissue spaces that are highly vascular. In contrast, TheraGauze/tobramycin will be placed into small (2 - 10ml) cutaneous abscesses where the bacterial infection has been walled off to protect the body from spread.

Tobramycin has also been used as a topical ophthalmic preparation for many years both as an ointment and drops (3 mg/ml) (e.g., Tobrex). Despite the very sensitive nature of topical application to the eye the package insert for Tobrex notes <1% hypersensitivity and eye or eyelid irritation is 3%, which is a typical rate for antibiotic eye drops. Additionally, Tobramycin eye drops (3 mg/ml) have been shown to have no adverse effects on reepithelialization and be well tolerated after penetrating keratoplasty (Blavin, Sauer et al. 2012)

Thus, there are several decades of human data demonstrating the safety of tobramycin when used topically for cutaneous and ocular wounds and in surgical wounds. The data suggests that local or systemic toxicity is extremely rare when tobramycin is used in these ways.

**Primary Endpoint.** The primary endpoint of the study is to evaluate the safety of and identify side effects of TheraGauze/tobramycin wound packing compared with standard of care management for cutaneous abscesses requiring incision and drainage.

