## Methods.

### Design:

This is a proof-of-concept, prospective, randomized clinical trial for safety of TheraGauze-tobramycin in adult subjects who present to Emergency Department settings for care of skin abscess requiring incision and drainage. A control, standard of care, arm is included to provide some data with respect to the side effect profile of current furunculosis management for comparison.

Two arms are proposed for this study:

1. Incision + TheraGauze+tobramycin packing (no systemic antibiotics)
2. Incision + standard iodoform wick or plain cotton wick packing ( $\pm$  p.o. antibiotics)

Anti-microbial TheraGauze (saturated with tobramycin ophthalmic solution at 3 mg/ml) will be packed into the drained wounds of the subjects in the study arm. The control arm will receive current standard of care wound packing with a choice of iodoform wick or plain cotton wick, based on the preference of the ED physician. After packing, the wound excess TheraGauze or wick will be cut away. The ED physicians have the option to prescribe an oral antibiotic or not,

according to their preference. The following oral antibiotic choices are available for subjects in the control arm only:

- Bactrim (TMP/SMX)
- Vibramycin (doxycycline)
- Cleocin (clindamycin)

Antibiotics will be purchased by subjects from their local pharmacy.

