- Currently taking or has taken oral or injection steroid medication (e.g. prednisone or Medrol Dosepak) in the past 30 (thirty) days

- Injection medications (Remicade, Humira, Cimzia, Simponi) other than vitamin (B6)
- Currently taking or has taken immune suppressing medications (e.g. methotrexate, Prograf, CellCept, Rapamune) in the past 30 (thirty) days
- Currently taking or has taken medications to treat cancer in the past 30 (thirty) days
- Subject is currently participating or has participated within the last two months in any study of an investigational drug or device.

*Recruitment and Retention:*

Subjects who present to Emergency Department setting for care of skin abscess requiring incision and drainage will be approached by on-site Study Coordinators for enrollment. The study coordinators and physician investigators are trained in obtaining informed consent. The potential subjects will be able to discuss participation with any family-member present, but due to the need for prompt treatment, the subject will need to make a decision regarding participate at the time of the Emergency Room visit. Upon meeting eligibility criteria and willingness to participate, subjects/LARs will provide informed consent. Complete demographic information to include residential and telephone contact information will be obtained. Prior relevant medical history and usual primary care contact information will also be collected. A medical information release will be obtained from the subject so that outcomes data can be collected related to additional unscheduled visits or adverse events cared for outside the emergency department setting.

*Women and minority participation:*

Adults up to 65 years of age will be enrolled regardless of gender and minority status as long as they are fluent in English.

*Randomization:*

A study subject identification number will be assigned. Subjects will then be sequentially randomized to one of two treatment arms upon enrollment in a 2:1 ratio, using a prepared list. Each subject's name will be recorded on the list next to his/her assigned subject number and randomization. For example, the first subject enrolled will be randomized to Treatment 1; the next enrolled subjects will be enrolled to Treatment 1; the third subject to Treatment 2. The fourth subject will be randomized to Treatment 1 and so on.

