    - Does wound require repacking? (y/n)
- Clinical Options
  - Return to ED for additional clinical evaluation and management (y/n)
      - Reason for reevaluation (infxn worsening/infxn non-improvement/other)
      - Another incision and drainage in the ED (y/n)
      - Addition of oral antibiotics (y/n)
      - Admission for i.v. Abx (y/n)
      - Admission for surgical intervention (y/n)
      - Return to ED in 2 more days (y/n)
- Schedule follow-up visit in Infectious Diseases Clinic at Children's Hospital of The King's Daughters (CHKD) in  $5 \pm 2$  days

Phone Follow up Contact Day Prior to CHKD visit:

Return visit reminder performed by Study Coordinator.

- Fever since leaving ED? (y/n, record temp if taken)
  - If prescribed, has antibiotic been taken (y/n, # doses)
  - If antibiotics taken, were any side-effects noted (y/n, list)
  - Increased or decreased pain (y/n, increased/decreased)
  - Increased or decreased size of redness (y/n, increased/decreased)
  - Any new symptoms? (y/n, list) Specific questions will include: presence of rash, loose stool, nausea, vomiting, abdominal discomfort, headache, dizziness, drowsiness, thrush, as well as any change in local signs or symptoms including pain and redness, new skin lesions, enlarged lymph nodes, and sore or white spots in the mouth.

Visit 3 - Day  $7 \pm 2$ : (CHKD Infectious Diseases Clinic):

Follow up on subjects' wound status. The following information will be collected and recorded on a hard copy Case Report Form at this contact.

- Questions about infection
  - Fever  $> 38^{\circ}\text{C}$  at home since incision? (y/n)
  - Pain (increased/same/decreased/resolved)
  - Redness (increased/same/decreased/resolved)
  - Persistent discharge (y/n)
  - Wound size (increased/same/decreased/resolved)
    - If resolved, day of wound closure (day)
  - New lesions since day 3 visit (y/n)
  - Was an p.o. antibiotic prescribed (y/n)
    - If yes, was the prescription filled (y/n)
    - How many doses have been taken so far? (##)
  - Any diarrhea? (y/n)
  - Any nausea or vomiting? (y/n)
  - Any abdominal discomfort? (y/n)
  - Any new rash? (y/n)

- Any other new symptoms including headache, dizziness, drowsiness, thrush, as well as any change in local symptoms.
- Wound assessment
  - Fever > 38°C in CRU? (y/n, record temp)
  - Packing present (y/n)
  - Diameter of erythema (mm) at widest diameter
  - Diameter of wound (mm) at widest diameter
  - Tenderness around the wound? (y/n)

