- Clinical Assessment (decided by PI or sub-I)
  - Infection worsening, non-improvement, improvement
- Clinical Options (decided by PI or sub-I)
  - No follow-up needed unless infection worsens
  - Suggest follow-up
- Clinical Follow-up, if applicable (obtained from subject or medical record after follow-up)
  - Another incision and drainage in the ED (y/n)
  - Addition of oral antibiotics (y/n)
  - Admission for i.v. Abx (y/n)
  - Admission for surgical intervention (y/n)
  - Return to ED in 2 more days (y/n)

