**Guidelines for Adverse Event Severity Assessments**

**Mild.** Minor awareness of signs or symptoms that are easily tolerated without specific medical intervention.

**Moderate.** Discomfort that interferes with usual activities and may require minimal intervention.

**Severe.** Significant signs or symptoms that are incapacitating with an inability to work or perform routine activities and/or that require medical intervention.

**Serious Adverse Events.** An SAE is any untoward medical occurrence that at any dose: is life threatening, requires in-patient hospitalization or prolongation of existing hospitalization, results in persistent or significant disability/incapacity. Important medical events may be considered serious when, based on appropriate medical judgment, they may jeopardize the subject and may require medical or surgical intervention to prevent one of the outcomes listed in this definition. If a serious and unexpected AE occurs for which there is evidence suggesting a causal relationship between the drug and the event the event must be reported as a serious and unexpected suspected adverse reaction. SAE will be reported to the local IRB and the FDA within 5 calendar days.

All unanticipated problems involving risk to subjects or others, serious adverse events related to participation in the study and subject deaths related to participation in the study should be promptly reported by [contact]), by email ([contact]), or by [contact]) to the USAMRMC, Office of Research Protections, Human Research Protection Office. A complete written report will follow the initial notification. In addition to the methods above, the complete report will be sent to the U.S. Army Medical Research and Materiel Command, ATTN: MCMR-ZB-PH, [name].

**Stopping Rules.** Adverse reactions, including local-toxicity adverse reactions, or SAEs will lead to immediate return to the SNGH ED for assessment and removal of the TheraGauze/tobramycin wound packing. The investigator will assess the need for treatment of the adverse reaction or SAE and, if necessary, either treat or refer for treatment, as appropriate. The subject will continue with their scheduled follow up: Day 3 visit in the ED, Day 6 phone follow up, and Day 7 visit in the CHKD Infectious Diseases Clinic

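### The last scheduled side-effect assessment can fall before a 7-day oral antibiotic course ends, so antibiotic side effects may be under-counted, mainly in the control arm

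*Combined protocol and SAP*

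**What the plan says.** The primary endpoint compares the safety and side effects of TheraGauze/tobramycin packing with those of standard care (Primary Endpoint). The Background describes that care as including "anti-MRSA systemic antibiotics given orally for 5 – 7 days" and puts diarrhea from these drugs at about 20%.

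The Methods fix no course length. Under Design: "The ED physicians have the option to prescribe an oral antibiotic or not". The share expected to receive a prescription is not given. Three drugs are listed under the line "The following oral antibiotic choices are available for subjects in the control arm only". The same section adds: "Antibiotics will be purchased by subjects from their local pharmacy". The first dose therefore follows discharge and may be delayed.

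TheraGauze/tobramycin is placed once and is due out at Visit 2 (Day 3 −1/+2, so Day 2 to Day 5). The Visit 2 form in Study Treatments also has a field for adding oral antibiotics, with no restriction by arm.

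Visit 3 is set at Day 7 ± 2 in Study Treatments and in the Study Visit Schedule. The Visit 2 instructions book it another way: "Schedule follow-up visit in Infectious Diseases Clinic at Children's Hospital of The King's Daughters (CHKD) in" 5 ± 2 days. The Stopping Rules list the remaining contacts as "Day 3 visit in the ED, Day 6 phone follow up, and Day 7 visit in the CHKD Infectious Diseases Clinic".

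Nothing is scheduled after Visit 3. The investigator chooses between "No follow-up needed unless infection worsens" and suggesting follow-up. The items recorded after that are repeat drainage, added antibiotics, admission and return to the ED, not side effects. Assessment of Safety gives no end date for adverse-event collection. Under Recruitment and Retention, a medical release is obtained so that "outcomes data can be collected related to additional unscheduled visits or adverse events cared for outside the emergency department setting".

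**The concern.** The control arm is there to show the side-effect profile of current management, and the Background names avoidance of systemic antibiotic side effects as the main likely benefit of the new packing. Antibiotic side effects are therefore central to what the trial is meant to measure.

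The two treatments are observed over different shares of their exposure. Planned packing exposure is always over by Visit 3. A 7-day antibiotic course need not be. Side effects that begin after the last contact are not asked about, so a true excess of antibiotic side effects among controls would look smaller than it is. The Statistical Analysis Plan declares equivalence when a 90% confidence interval lies within ±δ. It does not say which outcomes are tested and gives δ no value. If side effects are among those outcomes, the under-count would also make equivalence easier to declare.

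**Working it through.** **Inputs.** Course of 5 to 7 days and diarrhea about 20% (Background). Visit 2 on Day 2 to 5 and Visit 3 on Day 7 ± 2 (Study Treatments, Study Visit Schedule). Visit 3 booked 5 ± 2 days after Visit 2 (Study Treatments, Visit 2). 100 randomized 2:1, with 50 completing (Study Size). Day 1 is the day of treatment. Assumptions: antibiotics start on Day 1 or Day 2, and side-effect onset is spread evenly over the course.

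**1. Visit 3 window.** Directly: 7 − 2 = Day 5 to 7 + 2 = Day 9, nominal Day 7. By booking from Visit 2: earliest 2 + 3 = Day 5, nominal 3 + 5 = Day 8, latest 5 + 7 = Day 12. The two rules agree only on the earliest day.

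**2. Course days left after Visit 3.** Last course day = start + length − 1. Days left = max(0, last course day − Visit 3 day), counting the visit day as observed.

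| Course | Last day | Visit 3 on Day 5 | Day 6 | Day 7 | Day 8 | Day 9 |
|---|---|---|---|---|---|---|
| 5 days from Day 1 | 5 | 0 | 0 | 0 | 0 | 0 |
| 5 days from Day 2 | 6 | 1 | 0 | 0 | 0 | 0 |
| 7 days from Day 1 | 7 | 2 | 1 | 0 | 0 | 0 |
| 7 days from Day 2 | 8 | 3 | 2 | 1 | 0 | 0 |

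**3. Rate seen among those treated.** Rate = 0.20 × (1 − days left / length). For a 7-day course:

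- Visit 3 on Day 5: 0.20 × 5/7 = 14.3% (start Day 1) or 0.20 × 4/7 = 11.4% (start Day 2).
- Day 7: 20% or 0.20 × 6/7 = 17.1%.
- Day 8: 20% for both.

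For a 5-day course from Day 2 with Visit 3 on Day 5: 0.20 × 4/5 = 16%.

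**4. Counts in the worst case (7-day course, Visit 3 on Day 5).** Randomized controls: 100/3, about 33. If all are prescribed antibiotics, 33 × 0.20 = 6.6 expected cases would show as 6.6 × 5/7 = 4.7 or 6.6 × 4/7 = 3.8. If half are prescribed, 3.3 would show as 2.4 or 1.9. Among control completers (50/3, about 17), all prescribed: 3.4 would show as 2.4 or 1.9.

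**5. Antibiotics added at Visit 2, either arm.** Assume the same 5 to 7 days, started that day. If Visit 3 follows k days later, days left = max(0, length − 1 − k). For 7 days: 3 left at k = 3, 1 at k = 5, none from k = 6. For 5 days: 1 left at k = 3, none from k = 4. The latest such course runs to 5 + 7 − 1 = Day 11, at least 2 days past the Day 9 limit.

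**6. TheraGauze.** Planned exposure ends on Day 2 to Day 5, and Visit 3 is never before Day 5, so none of it lies beyond Visit 3.

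**The case against.** The strongest reply is that an early Visit 3 is unusual under the booking rule. Booked 5 days after a Day 3 visit, it falls on Day 8, which covers a 7-day course started on Day 1 or Day 2. Visit 2 has 4 permitted days and the interval 5, giving 20 combinations. Of these, 14 also meet Day 7 ± 2. Only 1 of the 14 gives Day 5, and 3 give Day 5 or 6. That stands. A reader who sees that 2 of the 5 permitted visit days precede the end of a 7-day course might infer a 40% risk. Neither count is a probability, and the documents give no distribution of visit days. But the Stopping Rules put the call on Day 6 and the visit on Day 7, when a 7-day course started on Day 2 is unfinished. A subject who takes that call and then misses Visit 3 is last heard from before any 7-day course ends.

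The 5 to 7 days is background text, and prescribing is optional. This also stands: it dilutes the effect by an unknown amount, but no other duration is available to plan around.

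Side effects are already asked about at two calls and two visits, and the medical release allows outside events to be collected. The calls and visits all end by Visit 3. The release reaches events that a clinician cared for, so mild diarrhea, nausea or rash managed at home would be missed.

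A reader might infer that the truncation affects the control arm only. The documents do not support that, because antibiotics can be added at Visit 2 in either arm. Nor do they support saying that the bias works against a formal hypothesis of fewer side effects with TheraGauze: the Background calls this a likely benefit, and the Statistical Analysis Plan specifies equivalence tests.

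**Conclusion.** The concern holds in a limited form. Followed exactly, the plan can stop asking about side effects during a 7-day course. A 5-day course started on Day 1 is covered on every permitted day, and a 7-day course started on Day 1 is covered from Day 7. The gap thus depends on a long course combined with an early visit or a late start. It falls mainly on controls who are prescribed antibiotics, and in either arm on those whose antibiotics are added at Visit 2.

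The direction for antibiotic side effects is toward no difference. The size runs from nothing at Day 8 to a 20% rate seen as 11.4% at Day 5. A reader might take the 11% to 14% as the expected result, but it is the worst case for a 7-day course. With about 17 control completers, all treated, even that amounts to 1.0 to 1.5 missed cases (3.4 − 2.4 and 3.4 − 1.9). These figures rest on even onset, starts on Day 1 or 2, and an unstated share prescribed. This is a cheap improvement to a pilot's primary comparison, not a flaw that invalidates it.

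**What to change.** Add one closing telephone contact by the study coordinator in both arms, timed after the longest antibiotic course described, including courses added at Visit 2. On the assumptions above, such a course can run to Day 11, or Day 12 if it is started a day late. Use the symptom list already written for the two existing calls. Define the side-effect collection period for the primary comparison as Day 1 to that call, identically in both arms.

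Reconcile the Visit 2 instruction that books Visit 3 5 ± 2 days later (nominal Day 8, range Day 5 to 12) with Day 7 ± 2 in the Visit 3 heading and the Study Visit Schedule.

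The cost is one short call per subject, with no change to treatment. Some subjects will not be reached, given the expected 50% retention, so the number reached should be reported by arm.
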